 - arterial stiffness (PWV and AI),
 - CGM measures of hyperglycemia, hypoglycemia, and glycemic variability for one week prior to each clamp,
 - Metabolic (NEFA, lipids, insulin, glucose), inflammatory (IL-6, TNF- α , hsCRP, adiponectin), thrombotic (PAI-1), oxidative stress (urinary isoprostanate, TBARs), and endothelial (ICAM, endothelin-1) markers at baseline each study day,
 - Counter-regulatory hormones (cortisol, growth hormone, glucagon, and catecholamines prior to each clamp,
 - Respiratory quotient at baseline and after low dose insulin infusion,
 - Heart rate variability,
 - Mitochondrial content (DNA and electron transport chain complexes),
 - Mitochondrial function (carbohydrate and lipid oxidation, max state 3 O₂ consumption, uncoupled O₂ consumption),
 - Mitochondrial state 3 O₂ consumption,
 - Mitochondrial oxidant generation (H₂O₂ production, glutathione redox state), and
 - Mitochondrial ATP production/ADP depletion by 31P-MRS.

[figure not shown]
B. Description of Population to be Enrolled: Study Design and Research Methods

Hypotheses: Metformin will improve (1) insulin action, (2) vascular function and compliance, and (3) mitochondrial function and oxidant generation in T1D subjects supporting a therapeutic role for metformin in T1D management, including CVD risk management.

Specific Aims: **Specific Aim 1:** Determine the effect of metformin on IR in T1D. **Specific Aim 2:** Determine the effect of metformin on vascular correlates of IR. **Specific Aim 3:** Determine the effect of metformin on mitochondrial function and oxidant generation.

Overall research plan: I propose to address these hypotheses and aims with a single-blinded, fixed-order, placebo-controlled cross-over design study in T1D subjects. The intervention will consist of 6 weeks of treatment with metformin, separated from the placebo period by a \geq 2 weeks washout period. The fixed order is needed because we and others have found persistent residual effects from metformin treatment, and the necessary washout period is not known. Metformin has been studied to a limited degree in T1D, primarily in terms of glycemic control. It has been found to be safe and well-tolerated in these studies (Vella) and the proposed dose and duration have precedent in the literature. [name] at this institution has performed a study using metformin in T1D youth. From his contact with the FDA, an IND is not required for this study.

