Sympathetic/parasympathetic balance: Respiratory heart rate variability by standard methods⁶⁰. Study participants will undergo supine resting electrocardiogram (ECG) recording for 5 minutes early in visits in a quiet room, with a stable room temperature. Participants will be asked to relax but not fall asleep and to breathe normally and remain still without talking during the ECG recording. Following the resting ECG, a second supine ECG will be recorded while study participants take in a deep breath for 10s. The ECG recordings will be transmitted electronically to the Epidemiological Cardiology Research Center (EPICARE) Center (Wake Forest University School of Medicine, Winston-Salem, NC) for analysis, interpretation, and calculation of heart rate variability. The SD of consecutive RR intervals of the entire record in Lead II will be used as a measure of overall HRV. In addition, autoregressive power spectral analysis will be used to determine the spectral power in the following bands: high frequency (HF, 0.15–0.45 Hz, reflects parasympathetic outflow), low frequency (LF, 0.04–0.15 Hz, reflects both sympathetic and parasympathetic outflow), and very low frequency (0.01–0.04 Hz). LF/HF and HF normalized to total power will be analyzed as measures of sympathetic and parasympathetic outflow, respectively.

Indirect calorimetry: For measurement of RQ fasting and during low infusion rate to assess insulin response of shift from fat to carbohydrate metabolism.

Muscle biopsy: Vastus lateralis muscle biopsies by the Bergstrom technique⁶⁹. Samples will be analyzed fresh for respirometry and H₂O₂ production; others will be flash frozen in liquid N₂ and stored at - 80° for PCR, glutathione assays, and immunoblotting. [name] does these biopsies regularly and will assist initially and train the PI in performance of these biopsies.

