Mitochondrial isolation, content, function, and oxidative stress: Respirometry of muscle tissue will be performed in isolated mitochondria by the method of Anderson et al⁷⁰ using the Oxygraph O2K respirometer. Portions of muscle tissue will be immediately homogenized and fresh mitochondrial preparations will be used to determine carbohydrate and lipid oxidation rates. Remaining tissue will be flash frozen in liquid nitrogen for appropriate analyses. Viable mitochondria will be isolated from fresh skeletal muscle tissue by trypsin collagenase digestion, homogenization and differential centrifugation by the methods developed by [name], consulting mentor. Mitochondrial protein concentrations will be determined using a bicinchoninic acid (BCA) assay. For mitochondrial assays, viable mitochondria will be introduced into the Oxygraph O2K chambers in duplicate with sequential addition of a combination of lipid and carbohydrate

substrates as well as physiological and chemical uncouplers, activators and inhibitors to gain a comprehensive view of metabolic and mitochondrial function in the physiological and supraphysiological energy states. A portion of the viable mitochondria isolated from the fresh tissue samples will also be used to assess hydrogen peroxide (H_2O_2) emission in the presence of the same substrates that were used in the mitochondrial respiration experiments. H_2O_2 is a common product of superoxide degradation and will be measured using a standard kit assay (Amplex Red®, Invitrogen), modified for mitochondria. A portion of the frozen tissue sample will be used to measure glutathione levels using a standard kit (Bioxytech® GSH/GSSG- 412TM, OxisResearch). The ratio of reduced to oxidized glutathione is a standard indicator of oxidative stress. Mitochondrial content is measured by QRT-PCR and blue native gel electrophoresis of isolated mitochondria.

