Quantitative Real Time PCR: Quantitative real-time PCR is performed with the Roche LightCycler 480 instrument and 480 SYBR Master mix for total mitochondrial DNA. Primer specificity is confirmed by melt curves. Relative abundance of mitochondrial DNA is quantified by standard curve method and normalized to the 18S rRNA gene as a chromosomal DNA marker.

³¹P-MRS: Methods: Calf MRS123-126: a 3.0 T whole-body MRI scanner (GE Medical Systems, Waukesha, WI), with a dual frequency ³¹P/¹H Flex Coil (Clinical MR Solutions) creates scout images of the dominant leg gastrocnemius and soleus muscles. The widest cross sectional area is fitted in the equation described in our preliminary results to determine expected force. A resistance strap is affixed to the hips, dominant leg, ankle and foot, on a specialized portable, in-MRI exercise bench to allow isolated static plantar flexion against force. Flexion is done at 70% of the subject's predicted maximal force for 90 seconds, monitored by a Single Point Load Cell (Teda Model 1250), connected via an A/D board to a laptop for analysis on LabView software. After scout images and shimming using the ¹H portion of the flex coil, ³¹P measurements are made at rest, during calf exercise, and for at least 15 min immediately following the exercise bout (figure 5). Total study time is < 1 hour. Output is analyzed using JmRUI and Sigma Stat to calculate PCr, phosphate (Pi), ADP, and ATP, which are used to calculate pH, ADP t_{1/2}, PCr t_{1/2}, Pi t_{1/2}, and substrate dependent (VPCr, Qmax, the apparent mitochondrial capacity i.e. maximal oxidative ATP production rate; anaerobic glycolysis; oxidative phosphorylation; CK, the non-mitochondrial dependent ATP production from creatinine kinase; muscle efficiency) and oxygen-dependent components (time constant for PCr, Pi & ADP recovery), allowing differentiation of substrate vs. oxygen-dependent causes of mitochondrial dysfunction. Primary outcomes for this portion of this sub-study will be QMax (max oxidative ATP production rate) and ADP depletion half-time.

Risks:

Continuous glucose monitoring: The continuous glucose monitor involves a small catheter placed under the skin in the area to the side of your belly. Potential risks of this procedure include bleeding, infection, pain, and catheter placement into a muscle causing pain and bruising.

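### Electron transport chain complexes count as mitochondrial content, but the gel that measures them is run on isolated mitochondria with no stated loading basis or yield correction

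*Combined protocol and SAP*

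**What the plan says.** Section IV.A, secondary outcomes, lists "Mitochondrial content (DNA and electron transport chain complexes" as one item. Mitochondrial function and oxidant generation are separate items.

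Section IV.D, paragraph on mitochondrial isolation, content, function and oxidative stress, gives the assays: "Mitochondrial content is measured by QRT-PCR and blue native gel electrophoresis of isolated mitochondria". The preparation is described earlier in that paragraph: "Viable mitochondria will be isolated from fresh skeletal muscle tissue by trypsin collagenase digestion, homogenization and differential centrifugation". Its protein concentration is measured by BCA assay. The paragraph does not say how the gel is loaded or what the bands are normalised to, and it does not relate the preparation to the mass of muscle it came from. On the rest of the biopsy it says: "Remaining tissue will be flash frozen in liquid nitrogen for appropriate analyses".

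Section IV.D, Muscle biopsy, divides the tissue. For the fresh part: "Samples will be analyzed fresh for respirometry and H₂O₂ production". For the rest: "others will be flash frozen in liquid N₂ and stored at - 80° for PCR, glutathione assays, and immunoblotting".

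Section IV.D, Quantitative Real Time PCR, has mitochondrial DNA "normalized to the 18S rRNA gene as a chromosomal DNA marker". Section IV.D, Immunoblot analysis, works from weighed frozen muscle cut into 30 mg pieces and homogenised, with 50 μg of protein run on the gel. It does not name the antibodies.

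Section F compares biopsy assays between the two periods in the same way as the other outcomes, by paired test, and adds no normalisation rule.

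**The concern.** Mitochondrial content means how much mitochondria the muscle holds. Once mitochondria have been separated from the muscle, the preparation no longer carries that information unless the amount recovered is tied back to the tissue it came from. The plan gives no such link for the gel.

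Respirometry and H₂O₂ emission are also measured in isolated mitochondria, so they do not show the amount in muscle either. Content is the biopsy outcome that would supply it. The background in IV.B cites a role for nitric oxide in mitochondrial biogenesis, so a change in amount is part of the protocol's own rationale.

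At stake is the reading of one component. A flat gel result could be reported as unchanged content when only composition was unchanged. If DNA and complexes then disagreed, it would look like a conflict between two measures of the same thing, when they measure different things.

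**Working it through.** The plan states no figure for this outcome, so there is none to reproduce. The check is how each readout responds to a change in muscle content.

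**Notation.** A = mg mitochondrial protein per g of muscle; k = amount of complex per mg mitochondrial protein; y = fraction of mitochondria recovered by isolation; w = g of muscle processed; L = mg mitochondrial protein loaded per lane. Subscripts 1 and 2 are the placebo and metformin visits. True complex content per g of muscle is A × k.

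**Gel, equal mitochondrial protein per lane (assumed).** Readout = L × k, so the ratio between visits is k₂/k₁. Neither A nor y appears. Take illustrative values A₁ = 5 and A₂ = 10 mg/g (assumed, not from the protocol), with k unchanged:

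- true ratio = (10 × k)/(5 × k) = 2.0
- gel ratio = k/k = 1.0

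A change in k would still show, so the readout is not fixed. It follows composition and misses amount.

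**Gel, loading tied to tissue mass (the alternative).** Readout = w × y × A × k. At equal w, the ratio is (y₂/y₁) × (A₂/A₁) × (k₂/k₁). With k unchanged:

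- A doubles and yield halves (assumed): 0.5 × 2 = 1.0, so a true doubling is hidden
- A unchanged and yield doubles (assumed): 2 × 1 = 2.0, an apparent doubling with no change in content

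This version does respond to amount, but it is multiplied by a yield ratio that the plan neither measures nor corrects. Every subject takes placebo first, so any drift in yield between visits would not be balanced by a reverse sequence.

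**DNA component.** Let M and N be mitochondrial and nuclear DNA in the tissue.

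- The biopsy paragraph sends frozen tissue to PCR, and mitochondria are isolated from fresh tissue. In whole frozen muscle the readout is M/N. If M doubles with N fixed, the ratio is 2.0, so it tracks content. The chromosomal 18S gene is a workable denominator there.
- If a laboratory instead took the words on isolated mitochondria to cover PCR as well, the readout would be (y/c) × (M/N), with c the fraction of nuclear DNA carried over. At fixed y, a c of 0.01 versus 0.02 (assumed) changes the result by 0.01/0.02 = 0.5 with no change in content. That would be unreliable, but it would still move with M.

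**Proposed measure.** In whole-muscle homogenate, complex per unit of total muscle protein is A × k/P, where P is total protein per g of muscle. With P and k unchanged, the ratio is (10k/P)/(5k/P) = 2.0, which matches the true change and does not involve y.

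**The case against.** The strongest reply concerns the DNA component. A reader might infer from the assay sentence that PCR too is run on isolated mitochondria, against a nuclear gene that isolation removes, so that the content outcome cannot respond at all. The documents do not support this. Frozen tissue is set aside "for PCR, glutathione assays, and immunoblotting", mitochondria come from fresh tissue, and a chromosomal denominator makes sense in whole muscle. The phrase on isolated mitochondria can attach to the gel alone, and that reading fits the other paragraphs. Even on the less likely reading the ratio would be unstable, not fixed. This part of the reply stands in full.

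Second, no loading basis is stated, so equal mitochondrial protein is an assumption. The BCA sentence does not mention gels. This is also right, and it rules out saying that a null result for the complexes is guaranteed. It does not rescue the gel, because the other natural basis, tissue mass, brings in yield uncorrected.

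Third, mtDNA/18S already gives a tissue-level content measure alongside the per-mitochondrion assays, so the plan can still separate amount from function. That stands and limits the harm to the complexes component.

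Fourth, section F calls secondary outcomes confirmatory or hypothesis-generating, and the study is powered only on the glucose infusion rate and flow-mediated dilation. That bears on severity. It does not make the gel a measure of content.

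**Conclusion.** The concern holds for the electron transport chain component only. As written, the gel does not measure the outcome it is assigned to. With equal mitochondrial protein per lane it reports composition and reads 1.0 for a true ratio of 2.0 at unchanged composition. With loading by tissue mass it is confounded by isolation yield. The sizes are illustrative and rest on assumed loading, content and yield; the protocol supplies no values. It would be wrong to conclude that every change in content is missed, or that the content outcome as a whole fails, because the DNA component is sound and the gel still responds to composition. The point is minor: one component of one secondary outcome is affected, and the primary outcomes, the sample size and the paired analysis are not.

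**What to change.** In section IV.D:

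1. Report the blue native gel as complex composition per unit of mitochondrial protein, state that loading basis, and stop labelling it as content.
2. Take mitochondrial content from whole frozen muscle: mtDNA/18S and, for the complexes, the homogenate immunoblot expressed per unit of total muscle protein. Add electron transport chain antibodies as a named target, since the immunoblot paragraph does not now specify them.
3. Reword the assay sentence so that PCR is plainly on DNA from frozen muscle, in line with the biopsy and PCR paragraphs.

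The secondary outcome in IV.A can then stay as it is, with complex composition listed separately. The cost is one added antibody target and some of the frozen tissue already being stored. No extra biopsy or visit is needed, and the analysis in section F does not change.

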active members) by mass mailing to the full cohort of an IRB-approved letter describing the study, followed by phone calls to invite questions. Although this cohort is an epidemiological outcome cohort, and the initial opinion was that this duration of intervention was inappropriate for such a study, funding pressures have influenced the CACTI PI to consider mechanistic studies and to agree that a short term metformin intervention is acceptable. In fact, a large grant to expand upon this pilot study is currently pending with the NIH. A strength of this study is thus access to the existing NIH-CACTI cohort that has been prospectively studied for ≥ 6 years. This is an active cohort with a great interest in diabetes and its management, and recruitment of 90 subjects for our recent clamp sub-study was easily accomplished.

Study population: The goal is to complete 30 T1D subjects (50% male in each group) for the pilot study. We expect to screen up to 100 subjects to enroll 40 and complete 30. Inclusion criteria:(1)age 20-59 years of age, (2) type 1 diabetes based on antibody-positivity, rapid persistent conversion to insulin requirement after diagnosis, absent C-peptide, or DKA at diagnosis, or a clinical course consistent with T1D, (3) HbA1c 6.0-9.5 (4) willing/able to commit to two 6 week-long study phases, each consisting of blinded medication with blinded CGM, frequent phone follow-up, and 3 days of prescribed diet followed by hyperinsulinemic euglycemic clamp, vascular testing, and 2 muscle biopsies. Exclusion criteria include:

[figure not shown]
- Any comorbid condition associated with inflammation, IR, or dyslipidemia
- Tobacco use
- Pregnancy
- Steroid use
- Scheduled vigorous physical activity >3 days a week
- Angina, known CAD, or any other cardiovascular or pulmonary disease
- A history of COPD or asthma
- Presence of systolic blood pressure >190 at rest or >250 with exercise or diastolic pressure >95 at rest or >105 with exercise
- Untreated thyroid disease
- Proteinuria (urine protein >200 mg/dl) or a creatinine ≥ 1.5 mg/dl(males) or 1.4 mg/dL (females), suggestive of severe renal disease
- Proliferative retinopathy.
- Niacin treatment
- Administration of experimental agent for T1D within 30 days prior to screening
- Recent (prior 6 months) or current metformin or thiazolidinedione use
- Hypoglycemia unawareness or recurrent severe hypoglycemia (no symptoms of hypoglycemia with FSBS<40 and episodes of this severity >1 per week)

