- Weight instability (weight change >5% in last 6 months)
- History of any organ transplant, including islet cell transplant
- Current or prior infection with HIV, hepatitis B or hepatitis C, or transaminases >2x ULN
- Any condition, medical or otherwise that would, in the opinion of the investigator, prevent complete participation in the study, or that would pose a significant hazard to the subject
- History of substance abuse within the 12 months prior to screening

Screening: A phone screen will be followed by provision of the consent form and a screening/enrollment visit at the outpatient CTRC. This visit will include the consent process, history, physical exam, non-fasting screening labs [β -HCG, HbA1c, metabolic panel, TSH, urine microalbumin, and CBC], detailed menstrual history for women, and a DEXA scan for body composition and estimation of caloric needs.

Study design:

T1D subjects (n=30) will have a fixed order of treatment (placebo-metformin) and will be given their first medication after screening is complete and eligibility confirmed. Medications (metformin 500, 1000mg and identical placebo) will be dispensed by the pharmacy and the subject will be blinded to the fixed order of the medications to avoid biased treatment effects throughout the intervention period. As in previous Barbara Davis Center (BDC) metformin studies, this study will use the CTRC pharmacy to dispense the active drug and placebo. Both are provided by Caraco manufacturer. My colleagues at the BDC already purchased tooling for the Caraco brand placebo tablets and the company has agreed to make more placebo tablets for this study as necessary to cut out the upfront cost of tooling.

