Subjects will be instructed to take study drug at 500mg at bedtime for the first week, 500 mg twice daily for the second week, 500/1000mg daily for one week and 1000mg twice daily for the remainder of the 6 week period. Subjects who fail to tolerate an uptitration will be held at the prior dose for an additional 3 days and then retried. Subjects who have not reached at least 500 mg BID dosing by the end of week 3 will be withdrawn from the study. Thus, final metformin dosing will be 500 BID or 1000 BID. During the last three days of each treatment phase, subjects will be placed on a standardized typical diabetic diet (40% carbohydrate, 35% fat, 25% protein; based on CACTI food records) for three days prior to late evening admission on day 3 to the CTRC. Overnight admission is critical to ensure that all subjects are in the same state prior to each testing session. Remaining pills will be turned in to allow a pill count as a measure of compliance. Subjects will be transitioned to an insulin drip for overnight glucose control using the protocol previously used for CTRC protocol 1499 (see appendices for starting doses and titration schedule). Inpatient studies (baseline labs, vascular studies, biopsies, and hyperinsulinemic euglycemic clamp) will be performed the following day (Figure 4). After a two week to two month washout period, the full cycle will be repeated with the second intervention. Women will be tested at the same time in their menstrual cycle (day 4-9) after each intervention period. Allowing up to 2 months between interventions is necessary to allow this type of scheduling with the possibility of a missed cycle due to scheduling conflicts. The study timeline and detailed visit schedule are as follows:

Screening:

- Visit 1: Screening visit - consent process, H&P, non-fasting labs, DEXA, dietary questionnaire

Stage 1 (Study drug A, Placebo):

- Visit 2: Stage 1 start visit (day A1) – Insert CGM and receive instruction on use and download, pick up Placebo, Instructions from PI re med dosing and insulin dose self-adjustment
- Visit 3: Stage 1 CGM follow-up visit (day A8) – in person CGM download and reinsertion of sensor for the next week. Review glucoses with PI.
- Visit 4: Stage 1 prestudy day visit (day A39) – pick up three day diet and receive instructions on insulin dosing and times for the pre-study day. Accelerometer set-up
- Visit 5: Admission for Placebo study day (Days A42, 43) – see below

2 weeks- 2 months wash-out

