Blood Draws: Pain may be felt when the needle goes into the vein. A bruise may form at the site. There is a risk of infection. Standard precautions will be used to minimize these risks and only CTRC nurses will perform blood draws.

Fasting: Subjects who are taking insulin run a risk of hypoglycemia during fasting. Fasting will only be required during the inpatient stays. Symptoms listed above will be described in advance and subjects will be monitored closely.

DEXA: During DEXA testing the amount of radiation received is less than 25mRem total body equivalent dose per measurement. This is estimated to be less than one-half the amount received from a chest x-ray. The radiation in this study is not expected to greatly increase these risks, but the exact increase in such risk is not known. Women who are or could be pregnant should receive no unnecessary radiation, and should not participate in this study.

IV Risks: When the needle carrying the plastic tube goes into a vein, it hurts for a short time. The needle is then removed and only the plastic tube remains in the vein. There will also be the minor discomfort of having the plastic tube taped to the arm. In about one in 10 cases a small amount of bleeding under the skin will produce a bruise. The risk of a blood clot forming in the vein is about one in 100, while the risk of infection or significant blood loss is one in 1000. Standard precautions will be used to minimize risk and only trained CTRC personnel will place IVs.

Arterial stiffness measurement and HRV measurements: There is a very slight chance that fainting or stroke may occur. No actual fainting or stroke have ever been reported. The risk of these happening has been estimated to be less than 1/1,000,000.

Brachial Artery FMD: There may be a slight discomfort while the arm cuff is inflated.

Muscle Biopsies: May be uncomfortable or cause pain. Infection, bleeding, or damage to nerves is reported to be 1/1000. The incision will be closed with a steri-strip or, if necessary, a single suture. A bruise may result temporarily, but a scar may be permanent. Numbing medicine will be used to reduce the pain. Rarely this causes an allergic reaction. A total of 2 muscle biopsies is required. Soreness or cramping in the muscle can occur during or after the procedure. Sometimes people faint.

Indirect calorimetry: Some people experience feelings of claustrophobia under the plexiglass hood used for these measurements.

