Though metformin is frequently taken during pregnancy, it is not fully proven safe in pregnancy and we will be excluding subjects who are pregnant or planning to get pregnant. Therefore, a pregnancy test will be done with the initial screening labs, and if a subject is pregnant or breastfeeding, she will be excluded from this study. If a subject becomes pregnant during the study she will be instructed to notify the study coordinator and withdraw from the study.

³¹P-MRS: Subjects may develop claustrophobia in the magnet or mild muscle cramping during the exercise portion

Unforeseen Risks: This study may include risks that are unknown at this time.

E. Potential Scientific Problems:

Interpretation of results/pitfalls and limitations: This study addresses the question of whether metformin affects insulin action and vascular and mitochondrial sequelae of IR in T1D. Based on the literature, I expect that GIR will be increased by this intervention, though it is unclear whether this will be mediated through changes in classical insulin signaling. An improvement in GIR would support the hypothesis that metformin is a viable approach to the treatment of IR in T1D that may have CVD benefits similar to those seen in T2D. If cardiovascular and/or mitochondrial measures improve (with or without changes in IR), this also lends support to metformin as a potentially CVD protective intervention and provides data to support a longer study looking at clinical outcomes. If no change in GIR or vascular measures occurs, this would suggest that IR and CVD risk in T1D are mechanistically different from other populations, an exciting result in itself, and future efforts would explore other mechanisms such as inflammation, sympathetic nervous system activation, and counter-regulatory hormones. Other outcomes will provide hypothesis-generating data to support and direct exploration of these other mechanisms of IR in T1D.

Other potential limitations of this study are:

- (1) Small size: it is possible that a smaller effect will occur in T1D than in other populations and this may therefore be missed in this small sample size.

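### The DEXA scan sits at Visit 1, before eligibility is confirmed and with no stated need for the pregnancy result first; it could move to Visit 2 without loss of planned data

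*Combined protocol and SAP*

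**What the plan says.** The Screening paragraph of Section IV.B describes the step before the scan: "A phone screen will be followed by provision of the consent form and a screening/enrollment visit at the outpatient CTRC". It then lists what that visit contains: consent, history, examination, non-fasting labs (including β-HCG, HbA1c, metabolic panel and TSH), and "detailed menstrual history for women, and a DEXA scan for body composition and estimation of caloric needs". The visit schedule in the same section agrees: "Visit 1: Screening visit - consent process, H&P, non-fasting labs, DEXA, dietary questionnaire".

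Eligibility is settled later. Under Study design, subjects "will be given their first medication after screening is complete and eligibility confirmed".

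The Study population paragraph gives the recruitment funnel: "We expect to screen up to 100 subjects to enroll 40 and complete 30".

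In the Risks part of Section IV.D, the DEXA paragraph puts the dose below 25 mRem per measurement, estimated at under half that of a chest x-ray, and adds: "Women who are or could be pregnant should receive no unnecessary radiation, and should not participate in this study". The pregnancy text later in that part says "a pregnancy test will be done with the initial screening labs".

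**The concern.** The scan is a screening procedure, yet it screens for nothing. None of the inclusion or exclusion criteria in Section IV.B depends on body composition or bone density. The labs drawn at the same visit do decide eligibility, through HbA1c, creatinine, transaminases, thyroid status and pregnancy. People who turn out to be ineligible, or who are eligible but do not go on, can therefore be exposed to radiation for a measurement that cannot enter the trial's data.

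A second, smaller matter concerns women. The pregnancy sample and the scan belong to the same visit, and nothing makes the scan wait for the result. Limitation (6) in Section IV.E says the investigator means to include pre- and perimenopausal women and not post-menopausal women. On that stated intent, the women screened are largely those in whom pregnancy cannot be excluded by menopausal status. What is at stake is avoidable low-dose exposure and an unsecured safeguard, not the validity of the results.

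**Working it through.** The documents state no number of DEXA scans, so there is no figure to reproduce. The check uses the protocol's own funnel and schedule.

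**Inputs**
- Screened up to 100, enrolled 40, completing 30 (Section IV.B, Study population). The Recruitment paragraph also has 40 starting.
- Dose below 25 mRem per scan (Section IV.D, Risks, DEXA).
- 50% male (Section IV.B, Recruitment, where it describes 100 eligible subjects). Applying it to everyone screened is an assumption.
- Visit 2 is Day A1; the three-day diet is collected at Visit 4, Day A39 (visit schedule).

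**Scans in people who never start**

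Ceiling = screened − started = 100 − 40 = 60, or 60/100 = 60%. It is reached only if all 100 attend Visit 1. The protocol gives no phone-screen failure rate and does not say whether its 100 counts phone screens or visits, so the range below is an assumption.

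| Of 100, stopped at phone screen | Scans at Visit 1 | Scans in non-starters |
|---|---|---|
| 0 | 100 | 60 |
| 10 | 90 | 50 |
| 25 | 75 | 35 |
| 50 | 50 | 10 |
| 60 | 40 | 0 |

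**Dose at the ceiling**
- All screened: 100 × 25, so below 2,500 person-mRem.
- Starters only: 40 × 25, so below 1,000 person-mRem.
- Difference: 60 × 25, so below 1,500 person-mRem.

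**Women**

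At 50% male, at most 0.5 × 100 = 50 women are scanned at Visit 1, of whom at most 0.5 × 60 = 30 never start. How many of them are or could be pregnant is not given.

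**Is the scan needed as early as Visit 1?**

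Its stated purpose there is "and a DEXA scan for body composition and estimation of caloric needs". The diet is first collected 39 − 1 = 38 days after Day A1. The documents do not say when caloric needs are calculated, but a scan on Day A1 would still precede the diet and both clamps. Body composition, bone density and any scaling of glucose infusion rate to fat-free mass (the unit used in the preliminary clamp data) would remain available for everyone who starts.

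**Order of pregnancy result and scan**

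Both descriptions of Visit 1 name the labs before the DEXA, but each is a list of contents. Neither is worded as a sequence, and neither sets a point at which the scan is held until a result is known.

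**The case against.** A reader might infer that up to 60 scans go against the protocol's own radiation statement. The documents do not support that. The sentence in the DEXA risk paragraph has a defined subject, women who are or could be pregnant. Scanning a man, or a woman who could not be pregnant, who later fails screening does not breach it. For them the point is a design choice about avoidable exposure.

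Nor do the documents show that women are scanned before their result is known. Reading the β-HCG first and scanning afterwards at the same visit fits every section. The text is silent on order, not contradictory.

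The size is also easily overstated. The phone screen comes before Visit 1, so 60 scans and 50 women are ceilings. The Recruitment paragraph describes the same 100 as eligible and enrolled. On that wording the 60 would be eligible people who did not start, and scanning ahead of eligibility would not explain them. The dose is low, and the protocol says it does not expect the radiation to raise risk greatly.

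Finally, moving the scan does not by itself protect women who could be pregnant. The interval between Visits 1 and 2 is not stated and no repeat test is specified, so relying on the Visit 1 result could lengthen the time from test to scan. A single sentence requiring the result before a Visit 1 scan would meet the safeguard without moving anything.

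All of this stands as a limit on the claim. It does not remove the main observation: the schedule permits scans in people who never start, for a measurement that decides nothing about their entry. The one-sentence alternative would leave most of those scans in place.

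**Conclusion.** The point holds as a low-cost improvement to the schedule. The DEXA is part of screening, eligibility is confirmed only once screening is complete, and no criterion uses the scan. Scans in non-starters number between 0 and 60, depending on phone-screen losses that the protocol does not state. The ceiling assumes that all 100 attend Visit 1 and that 40 start. Separately, no step in the schedule guarantees the protection that the DEXA risk paragraph intends for women who are or could be pregnant. That is missing detail and not a contradiction. Neither part touches power, the type I error rate, the endpoints or the analysis.

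**What to change.** 1. Remove the DEXA from the Screening paragraph and from the Visit 1 line, and list it at Visit 2 (Day A1), after eligibility is confirmed.
2. State that a pregnancy result must be available before the scan, and say which result applies, because the Visit 1 to Visit 2 interval is open. The Screening paragraph, the visit schedule, the DEXA risk paragraph and the pregnancy text under Risks would then agree.
3. Reconcile the Recruitment and Study population paragraphs on whether the 100 are screened or are eligible and enrolled.

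With 40 starters, scans fall from at most 100 to at most 40. The cost is a change of wording, a slightly longer Visit 2, and the need to specify the applicable pregnancy result. No planned data are lost.
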